#### **Secondary Objectives**

To assess acute side effects from irradiation using proton beam therapy for the treatment of chordomas or chondrosarcomas.

To assess late complications from irradiation using proton beam therapy for the treatment of chordomas or chondrosarcomas.

To compare the dose distribution to tumor and surrounding normal structures using DVH's (Dose Volume Histograms) generated from the proton plan used to treat the patient and the photon plan generated for comparison purposes.

To monitor the rates of local control as well as overall and disease specific survival using proton radiotherapy.

Version: 04/04/2014

To evaluate the time to progression and progression free survival of chordomas or chondrosarcomas treated with protons.

To evaluate the effect of proton beam radiation on neurocognitive outcome in patients with chordomas or chondrosarcomas.

To evaluate the quality of life (e.g., fatigue) in patients treated for chordomas or chondrosarcomas.

# 3 Subject Selection and Withdrawal

This study plans to enroll 50 subjects over a 4 year period of time. We plan to enroll male and female subjects of all races.

#### 3.1 Inclusion Criteria

- Histologically confirmed diagnosis of chordoma or chondrosarcoma.
- Patients must have no evidence of metastatic disease based on routine imaging (Chest x-ray, CT or MRI of the chest/abdomen/pelvis, bone scan, etc).
- Patients must have an ECOG score equal to or less than 2.
- Age  $\geq$  18.
- Patients must be able to provide informed consent.
- Women of child-bearing potential as long as she agrees to use a recognized method of birth control (e.g. oral contraceptive, IUD, condoms or other barrier methods etc.). Hysterectomy or menopause must be clinically documented.
- Tumors arising in the skull and spine.

#### **3.2** Exclusion Criteria

- Prior or simultaneous malignancies within the past two years (other than cutaneous squamous or basal cell carcinoma, melanoma in situ or thyroid carcinoma)
- Patients with the following histologies are excluded: melanoma, other soft tissue or bony sarcomas, giant cell tumor, aneurismal bone cyst or metastatic lesions from other histologies.
- Pregnant women.
- Actively being treated on any other therapeutic research study.
- Tumors arising outside of the CNS.

# 3.3 Subject Recruitment and Screening

Subjects will be recruited from either the Department of Defense (DOD) Oncology practices or the Department of Radiation Oncology, Neurosurgery and Otorhinolaryngology practices at The University of Pennsylvania Medical Center (Hospital of the University of Pennsylvania, Pennsylvania Hospital and Penn Presbyterian Medical Center). The treating radiation oncologist will determine if the patient is a potential research candidate and has the capacity to consent. The treating radiation oncologist will approach and inform the patient about the study, thereby initiating the informed consent process. If the patient expresses interest in the study, the treating radiation oncologist will contact a qualified member of the research team in the Radiation Oncology department at the University of Pennsylvania and request availability for

enrollment. A qualified member of the research team will interview the potential subject with privacy considerations, explain the requirements of the study and provide a copy of the Informed Consent Form (ICF). The person obtaining consent will state the volunteer nature of research and advise the subject to take sufficient time to discuss the study if necessary before making their decision to sign the informed consent document. If a decision to participate is made, the informed consent form is signed after which any screening procedures will be performed. A series of questions will be asked by the person obtaining consent to verify patient eligibility based upon the criteria outlined in Section 3.1 and Section 3.2. After the eligibility is established, a subject study number will be issued. Eligibility is confirmed with the study investigator. All members of the research team will have successfully completed patient oriented research training. Subjects will receive all treatment in the Radiation Oncology clinic of the University of Pennsylvania.

At the University of Pennsylvania, we see approximately 12 cases of chordoma and/or chondrosarcoma per year. We anticipate that with the availability of proton radiotherapy, these numbers may increase. We estimate an annual accrual of 12-15 subjects per year. Proton radiotherapy will be listed on our web site and in Oncolink as a formal protocol and information of its availability will be made known to treating professionals throughout our satellites and referring physicians.

### **3.4** Early Withdrawal of Subjects

### 3.4.1 When and How to Withdraw Subjects

- Recurrent or Progressive Disease: Subjects who have clinical or radiologic evidence of recurrent disease will undergo an evaluation to document the nature of the abnormality. If recurrent or progressive cancer is diagnosed, the subject will be considered off study at that time.
- PI Decision: Subjects may be withdrawn at any time during the study if the PI believes it is in the subject's best interest. In this event, the reasons for withdrawal will be documented.
- Subject Participation: Refusal to continue treatment, follow-up, comply with the protocol or withdrawal of consent. In this event, the reasons for withdrawal will be documented.
- Adverse Event (including intercurrent illness, unacceptable toxicity).

Once the subject has discontinued treatment, the primary reason for discontinuing treatment must be clearly documented in the subject's records and on the CRF. The investigator will assess each subject for response at the time of withdrawal.

Every effort will be made to follow all subjects off study for toxicity and survival unless patient withdraws consent. If subjects withdraw from the study at any time, we will ask for his/her written permission to continue to access medical records for overall survival. Acute toxicities will be assessed for 90 days from the first date of treatment. Survival will be followed for a minimum of 5 years.

# 4 Radiation Therapy

### 4.1 Treatment Planning, Imaging and Localization Requirements

- **4.1.1** All subjects will be immobilized in a custom designed device in the appropriate position.
- **4.1.2** Radiotherapy treatment planning CT scans and MRI scans will be required to define gross tumor volume (GTV) and clinical target volume (CTV). The treatment planning CT scan (or MRI scan) should be acquired with the subject in the same position and using the same immobilization device as for treatment. Treatment planning will be done using a 3D based CT or MRI treatment planning system. All tissues to be irradiated must be included in the CT/MRI scan. Planning CT/MRI scan will be done at 1.5 mm intervals depending on the site of disease (craniospinal axis). A second treatment planning CT/MRI scan may be performed during the course of radiotherapy as necessary. Imaging including FDG-PET/CT and/or MR imaging maybe fused with the planning CT images to better visualize the anatomy when indicated.

# 4.2 Target Contouring

- **4.2.1** Gross Tumor Volume (GTV) is defined as all known gross disease determined from CT, MRI, and PET imaging.
- **4.2.2** Clinical Target Volume (CTV) is defined as the GTV plus areas that are considered to contain potential microscopic disease (the operative site and other areas of microscopic risk).
- 4.3 After delineating the CTV, the margins are added to the CTV by means of enlarging the beam aperture both laterally and cephalo-caudally in the beam's eye view, and the distal and proximal margins are calculated and added. These margins cover the uncertainty due to range, set-up errors and lateral fall off of the irradiation fields. A compensator is created to control the axial dose deposition distally. Smearing and border smoothing will be routinely calculated and applied. Compensator editing may be necessary to deliver the dose as prescribed by the physician. All the above parameters are calculated and

recorded by the planner under the physicist supervision and are subject to discussion with the physician as appropriate. Review volumes called RC-review = CTV + 0.2 or 0.3 cm are created in order to facilitate the coverage evaluation process. For pencil beam scanning treatment planning, a PBSTV will be employed for treatment planning optimization purposes. All these parameters can be altered by the radiation oncology team as appropriate in order to deliver the prescribed dose and maintain sparing of the organs at risk (OAR). Normal Structures

- 1. Optic nerves
- 2. Optic chiasm
- 3. Eye
- 4. Lens
- 5. Brainstem
- 6. Cochlea
- 7. Spinal cord
- 8. Right and left hippocampus
- 9. Pituitary
- 10. Temporal lobes
- 11. Cerebellum
- 12. Hypothalamus
- **4.3.1** The dosimetrist will define two structures: Skin-2 (2mm thick surface) and Skin-RC-REVIEW\_Review (all RC-REVIEWs subtracted from the surface contour). Skin-RC-review is the normal tissue structure is all tissue other than what is contoured as something else.
- **4.3.2** Organ at risk volume (OAR) is contoured as visualized on the planning CT or MR scan. Planning PAR is the OAR expanded for set-up uncertainty or organ motion. The physician will contour the OAR. The dosimetrist may create the PAR by expanding the OAR by 2-3 mm, depending on the situation.

The following structures will be contoured (depending on location of primary tumor):

CNS (BOS): spinal cord, brainstem, optic nerve (right/left), optic chiasm, eye (right/left), lens (right/left), cochlea (right/left), right and left hippocampus, pituitary, cerebellum, temporal lobes.

*Head and neck (Cervical spine):* salivary glands (parotid-right/left, submandibular right/left), larynx, oral cavity, upper esophagus, mandible, lungs, brachial plexus.

Spine (Thoracic/Lumbosacral): spinal cord, thecal sac.

# **4.4** Dose fractionation and specification

#### 4.4.1 Dose

For chordomas, the total dose will be 72.00 to 79.2 Gy (RBE) in 40-44 fractions at 1.8 Gy (RBE) per fraction. For chondrosarcomas, the total dose will be 70.20-73.80 Gy(RBE) in 39-41 fractions at 1.80 Gy(RBE) per fraction. Proton and photon therapy will be prescribed upon consultation with Physics in order to ensure a robust plan.

Version: 04/04/2014

Doses throughout will be prescribed as Gray (Gy) for any IMRT (if used) and in Gy Relative Biologic Effectiveness (RBE) for the proton treatment. The total dose will be the addition of the treatment received with IMRT (if used) and proton therapy. One Gy will be the equivalent of one Gy (RBE).

# 4.5 Treatment Planning

**4.5.1** Dose specifications: 98% of CTV must be covered 95% of the dose. 100% of the GTV should be covered by at least 97% of the dose. A 1% deviation is acceptable. Larger deviations may be necessary due to target proximity to the brainstem/cord and they can be accepted after analyzing the case with the treating physician

**4.5.2** Dose Constraints for organs at risk (OARs):

1. Optic nerves	62.00 Gy (RBE) (max dose, less than 0.03 cc)
2. Optic chiasm	62.00 Gy (RBE) (max dose, less than 0.03 cc)

3. Eye
 4. Lens

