# 2 Study Objectives

This study will be done in two phases. In the first phase, feasibility will be established using the primary objectives set below. The second phase will begin no earlier than 90 days after the last patient in the initial phase has started treatment and once safety and feasibility has been verified. The secondary objectives will serve as the objectives for the second phase of the study.

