#### **Primary Objective**

The primary objective of this study is feasibility. The study will be deemed infeasible if greater than 10% of pts experience one of the following:

- a. Patient cannot be given treatment because anatomy is such that a dosimetrically satisfactory treatment plan cannot be devised as defined in Section 4.5.1.
- b. For base of skull patients only. Patient receives greater than 40% of their total treatment (for any reason, i.e. unable to set patient up within acceptable limits of tolerance, patient unable to tolerate treatment position or immobilization for duration of treatment) with photon beam radiotherapy (using a backup photon plan).

For spine and all other patients. Patient receives greater than 20% of their total treatment (for any reason, i.e. unable to set patient up within acceptable limits of tolerance, patient unable to tolerate treatment position or immobilization for duration of treatment) with photon beam radiotherapy (using a backup photon plan).

- c. Patient is unable to complete all of his/her treatments within 10 days of estimated date of treatment completion or requires a treatment break greater than 5 days.
- d. Additionally, no greater than 20% of patients experience an unexpected acute toxicity > Grade 3 that is probably or definitely related to radiation therapy.

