 10.00 Gy (RBE)
 4.00 Gy (RBE)

5. Brainstem 67.00 Gy(RBE) to the anterior surface, 55.00 Gy (RBE) to the

center and 50.00 Gy (RBE) to the posterior surface

6. Cochlea 60.00 Gy (RBE) (point dose, 30.00 Gy (RBE) to the contralateral,

if well lateralized lesion

7. Spinal cord 45.00 Gy (RBE) (if base of skull primary; same constraints as

brain stem if spinal cord primary)

8. Pituitary 45.00 Gy (RBE)

9. Temporal Lobes Less than 10% to get prescription dose 10. Cerebellum Less than 10% to get prescription dose

Note: All planning parameters can be altered by the radiation oncology team as appropriate in order to deliver the prescribed dose and maintain sparing of the organs at risk if clinically acceptable to the treating physician

4.5.2 IMRT backup plans or partial treatments may be carried out as requested by the physician. The prescription is as specified above and administered using the same scheme. The planning target volume expansion margin defined on case by case basis from the CTV volumes .The lateral margins will be defined by the multi-leaf collimator and will wary between 0.3 to 1.5 cm or as found to be appropriate in order to have adequate coverage to sparing ratio.

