#### 7.1 FEASIBILITY STUDY

# 7.1.1 Design and Objectives

The primary objectives are to determine feasibility and safety (acute toxicity). Secondary objectives are to determine late toxicity, long-term clinical outcomes and, fatigue and neurocognitive function.

Twelve patients will be enrolled and followed for a minimum of 90 days after start of radiotherapy to determine feasibility and acute toxicity. We expect to screen/enroll approximately 18 subjects to reach the goal of 12 evaluable subjects. A subject will be considered evaluable if they willingly remain on the study up until their first follow up visit. [note: a subject is still evaluable even if they are unable to undergo proton treatment as defined in section 2.0 or have a significant acute toxicity as these are feasibility criteria]. Ninety days of observation after start of radiotherapy will be required in all 12 patients prior to commencing the second phase of the trial. Patients enrolled in the feasibility study will continue to be followed beyond 90 days for the secondary endpoints of late toxicity, progression-free and overall survival fatigue and neurocognitive function.

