### 7.1.2 Endpoints

### 7.1.2.1 Primary Endpoints

Feasibility will be based on multiple radiation planning and treatment parameters. For proton to be deemed feasible, no greater than 10% of patients should experience one of the following events: a) Patient cannot be given treatment because anatomy is such that a dosimetrically satisfactory treatment plan cannot be devised. For example, the dosimetry is unsatisfactory if

<95% of target volume is covered by 95% of the dose, b) Patient receives greater than 50% of their total treatment (for any reason-unable to set patient up within acceptable limits of tolerance, patient unable to tolerate treatment position or immobilization for duration of treatment) with photon beam radiotherapy (using a backup photon plan, c) Patient is unable to complete all of his/her treatments within 10 days of estimated date of treatment completion or requires a treatment break greater than 5 days.

Acute Toxicity is defined as any grade 3 or higher toxicity, considered probably or definitely related to radiation, observed within 90 days from start of therapy, excluding cranial nerve palsies or nerve root symptoms as these may be due to the tumor itself or prior surgery. Toxicities will be graded using the NCI Common Terminology Criteria for Adverse Events (CTCAE) Version 4.0.

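### Component (a) of the primary feasibility endpoint carries two inconsistent dosimetric tests: Section 4.5.1 (adopted by Section 2) and the coverage example in Section 7.1.2.1 (minor)

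*Combined protocol and SAP*

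**What the plan says.** Section 2 opens by saying "In the first phase, feasibility will be established using the primary objectives set below". Its item (a) is a patient who cannot be treated because "a dosimetrically satisfactory treatment plan cannot be devised as defined in Section 4.5.1".

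Section 4.5.1 sets the standard: "98% of CTV must be covered 95% of the dose. 100% of the GTV should be covered by at least 97% of the dose". The section tolerates deviations of 1%. On larger ones it says: "Larger deviations may be necessary due to target proximity to the brainstem/cord and they can be accepted after analyzing the case". The analysis is made with the treating physician, and no lower limit on coverage is given.

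Section 7.1.2.1 restates component (a) as part of the primary endpoint without citing 4.5.1. It illustrates the component instead, with the lead-in "For example, the dosimetry is unsatisfactory if" and then the condition "<95% of target volume is covered by 95% of the dose". *Target volume* is not defined there. Section 4 uses several volumes, including GTV, CTV and, for pencil beam planning, PBSTV.

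Section 7.1.1, on who is evaluable, points back to Section 2: "a subject is still evaluable even if they are unable to undergo proton treatment as defined in section 2.0".

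The component feeds the 10% limit on infeasible patients, the Bayesian termination table in 7.1.3, and the posterior probability in 7.1.4 that the feasibility rate exceeds 90%.

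**The concern.** One component of the primary endpoint should have one test. Here the protocol's objectives and the statistical section give different coverage thresholds, and only one of them has an exception. No clause says which prevails.

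Patient numbers are small: 12 in the original feasibility cohort, and up to 17 after the amendment (12 base of skull, 5 spine). One or two patients classified differently would therefore move the reported result. The test can also matter before scoring. If planners use it to decide whether an acceptable plan exists, it determines who is treated and so who becomes an event.

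**Working it through.** **1. The two tests side by side**

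| Feature | Section 4.5.1, adopted by 2(a) | Example in 7.1.2.1(a) |
|---|---|---|
| Volume | CTV and GTV | *Target volume*, undefined |
| Coverage at 95% of dose | 98% of CTV | Unsatisfactory below 95% |
| GTV condition | 100% at 97% of dose or more | None |
| Tolerance | 1% | None |
| Brainstem/cord exception | Yes, no floor | None |
| Status of wording | Definition | Illustration |

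**2. Where they disagree, taking the undefined volume to be the CTV**

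- *CTV coverage below 95%, accepted for brainstem or cord proximity* (say 93%): satisfactory under 4.5.1, unsatisfactory under the example.
- *CTV coverage from 95% to just under 97%, with no such reason*: fails 4.5.1 if the 1% is read as volume (98% − 1% = 97%), but is not flagged by the example. This direction arises only if the example is used as the cut-off. An example of what is unsatisfactory does not make everything above it satisfactory.

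**3. Could the exception be needed?** Inputs are the prescriptions in 4.4.1 and the brainstem limit in 4.5.2, "67.00 Gy(RBE) to the anterior surface".

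- Chordoma, 95% of prescription: 0.95 × 72.0 = 68.40 Gy to 0.95 × 79.2 = 75.24 Gy.
- Chondrosarcoma, 95% of prescription: 0.95 × 70.2 = 66.69 Gy to 0.95 × 73.8 = 70.11 Gy.
- The limit as a share of prescription: 67/79.2 = 84.6% to 67/72.0 = 93.1% for chordoma; 67/73.8 = 90.8% to 67/70.2 = 95.4% for chondrosarcoma.

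If the CTV touches the anterior brainstem surface and the limit is held, the coverage dose cannot be reached at the point of contact, except at the 39-fraction chondrosarcoma dose (66.69 Gy). So the exception is foreseeable. The documents do not show how much of any CTV would be underdosed.

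**4. Scale of reclassifying a patient.** With the beta(5,1) prior of 7.1.3 and x feasible patients out of n, the posterior is Beta(5 + x, 1 + n − x), and the quantity of interest is P(rate > 0.90).

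The plan's own table first: 1 of 3, 4 of 6, 6 of 9 and 9 of 12 give 0.038, 0.090, 0.044 and 0.083. These match the stated 0.04, 0.09, 0.04 and 0.08.

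Now let k patients be counted infeasible, with no other event. The value of k is an assumption. With k = 0 the formula reduces to 1 − 0.9^(5+n).

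| k | n = 12 | n = 17 | n = 26 |
|---|---|---|---|
| 0 | 0.833 (0%) | 0.902 (0%) | 0.962 (0%) |
| 1 | 0.518 (8.3%) | 0.661 (5.9%) | 0.830 (3.8%) |
| 2 | 0.238 (16.7%) | 0.380 (11.8%) | 0.611 (7.7%) |
| 3 | 0.083 (25.0%) | 0.172 (17.6%) | 0.376 (11.5%) |

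Brackets show the infeasible share, to compare with the 10% limit. That limit is first exceeded at k = 2 for n = 12 and n = 17, and at k = 3 for n = 26. At n = 12, k = 3 is the termination row. Any reclassification of k patients, for whatever reason, gives these shifts. They do not show that the wording conflict would cause one.

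**The case against.** The strongest reply is that the event text already settles the patient in question. Both 2(a) and 7.1.2.1(a) require that the patient could not be treated. Someone treated on a plan accepted under the exception was treated, so on the literal wording is not an event under either section. The example labels dosimetry; it does not remove that condition. This largely stands. A reader might infer that treated exception patients would be counted infeasible and the rate biased downward, or the termination rule triggered. The documents do not support that.

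Second, 4.5.1 is given as a definition and 7.1.2.1 as an illustration, and Sections 2 and 7.1.1 both point to Section 2. This stands as the natural reading, although no precedence clause exists.

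Third, a reader might infer from the dose figures that the exception is unavoidable in base of skull patients. It is not shown. A note in 4.5.2 allows planning parameters to be altered, so 67 Gy (RBE) is not a fixed ceiling. Contact at a surface does not establish that more than 5% of a CTV is underdosed. Twelve base of skull patients are not twelve exception plans.

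Fourth, the photon limit in component (b) also differs: 50% in 7.1.2.1 against 40% (base of skull) and 20% (others) in Section 2. This suggests that 7.1.2.1 was not aligned with Section 2, but the document does not mark it as superseded. It argues for correcting both items together.

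What survives is narrower. Whether an acceptable plan exists is itself the decision that (a) turns on, and the current text offers two thresholds for making it.

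**Conclusion.** The inconsistency is real and lies in the current text; its severity is minor. One component of the primary endpoint has two dosimetric tests that can disagree in both directions, and the statistical section neither cites the definition nor names the volume. Section 2(a) with 4.5.1 is the more natural governing text, and a patient treated on an accepted exception plan is probably not an event under either section. The practical effect is therefore likely small. Its frequency and direction cannot be derived from the documents.

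The conclusion rests on reading the undefined volume as the CTV and, for the 95% to under 97% band, on reading the 1% as volume and using the example as the cut-off. The posterior figures show only how sensitive a small cohort is to a single patient. The n = 26 column is looser still, because 7.1.4 scores each patient by the definition in force at that patient's enrolment, so one wording need not apply to all 26.

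**What to change.** In 7.1.2.1(a), delete the coverage example and refer to Section 2(a) and 4.5.1. In the same amendment, bring the photon limit in (b) into line with Section 2.

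State explicitly that a patient treated on a plan accepted under the brainstem/cord exception counts as feasible for (a).

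Report the number of exception plans with the CTV and GTV coverage achieved. Because the exception has no floor, readers otherwise cannot see how many feasible patients depended on it.

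Apply the change prospectively, in keeping with the 7.1.4 rule on the definition in force at enrolment.

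The cost is a short amendment and one small table. For component (a), treatment, sample size and the termination boundaries are unchanged.
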